17.3 Subject confidentiality

The trial staff should ensure that the subject's anonymity is maintained. The subjects will be identified by a subject ID number in the CRF and any electronic database owned by ALK. All documents will be stored securely and only accessible by trial staff and authorised personnel.

17.4 Data protection

All data will be handled and stored according to GDPR (The European parliament 2016).

Investigator

Clinical trial protocol Trial ID: SU-G-01	Date: Version:	12-Nov-2021 4.0	11	
EudraCT No. 2020-000455-12 CONFIDENTIAL	Status: Page:	Final 69 of 77		

By signing this protocol, the investigator recognises that certain personal identifying information with respect to the investigator and all sub-investigators and trial site personnel, may be used and disclosed for trial management purposes, as part of a regulatory submissions, and as required by law. This information may include:

- Name, address, telephone number and email address
- Hospital or clinic address and telephone number
- Curriculum vitae or other summary of qualifications and credentials
- Financial disclosure information
- Other professional documentation

Consistent with the purposes described above, this information may be transmitted to ALK, affiliates and ALK representative, in the investigator's country and other countries, including countries that do not have laws protecting such information. In these cases, ALK will take appropriate measures to protect data and ensure that the transfer of data will have an adequate level of data protection. ALK will rely on valid standard contract clauses signed with third parties.

Additionally, the investigator's name and business contact information may be included when reporting certain SAEs to regulatory authorities or to other investigators. By signing this protocol, the investigator expressly consents to these uses and disclosures.

If this is a multi-site trial, in order to facilitate contact between investigators, ALK may share an investigator's name and contact information with other participating investigators upon request.

Subjects

Subjects will be assigned a unique identifier, a subject number. Any subject records or datasets that are transferred to ALK will contain the identifier only; subject names or any information which would make the subject identifiable will not be transferred. This way the subject data will go through a pseudonymisation process, which means that the data cannot be attributed to a specific subject without the use of additional information.

The subject and any biological material obtained from the subject will be identified by subject number, visit number and trial ID. Appropriate measures such as encryption or leaving out certain identifiers will be enforced to protect the identity of subjects as required by local, regional and national requirements.

The subject must be informed that his/her personal trial related data will be used by ALK in accordance with local data protection law. The disclosure of the data must also be explained to the subject.

The subject must be informed that his/her medical records may be examined by auditors or other authorised personnel appointed by ALK, by appropriate IRB/IEC members, and by inspectors from regulatory authorities.

Transfer of data

If data are transferred to or accessed by third countries, that is, countries outside EU/EEA countries, the data will be protected to have an adequate level of data protection principles.

Description of arrangements

To ensure the safekeeping of clinical trial data ALK has Standard Operating Procedures that defines how data shall be managed including handling of security data breaches. When data is

Clinical trial protocol Trial ID: SU-G-01 EudraCT No. 2020-000455-12 CONFIDENTIAL	Date: Version: Status: Page:	12-Nov-2021 4.0 Final 70 of 77	<
CONFIDENTIAL	гауе.	70 01 77	

managed by external parties, written agreements are in place to ensure that the data is handled according to ALK's instructions/standards.

17.5 IEC/IRB/regulatory authorities

Before initiation of this trial, the protocol, the proposed informed consent form and other information to subjects as well as other documents required, must be reviewed by a properly constituted IEC/IRB and provided to the national (and local, if applicable) regulatory authority.

A signed and dated statement that the protocol and the subject information sheet/informed consent form and any other information to the subjects have been approved by the IEC/IRB and the regulatory authority must be obtained before trial initiation.

17.6 Inspections

An IEC/IRB or a national or international regulatory authority may also wish to conduct an inspection (during the trial or after its completion). If an inspection is requested by a regulatory authority, the investigator must inform ALK of the request immediately. The investigator or ALK should agree (in accordance with the prevailing law) with the inspectors that ALK shall have the right to be present at any inspection or investigation. The investigator or ALK should agree with the inspector that ALK may conduct and control applicable action arising from the inspections at ALK's expense.

The investigator must be available during the inspection and give the inspectors direct and unlimited access to source documentation and data, records and reports used, referenced or created as part of performance of this trial.

17.7 Protocol amendment and other changes in trial conduct

Substantial changes to this protocol require a protocol amendment that must be signed off by ALK and the investigator(s) and be approved by IEC/IRB and/or regulatory authorities as applicable before implementation.

The requirements for approval of the substantial changes should in no way prevent any immediate action from being taken by the investigator or by ALK in the interest of preserving the safety of all subjects included in the trial.

Amendments not considered substantial such as administrative changes will only be submitted to the regulatory authorities once another substantial amendment must be submitted or together with the end of trial notification unless national legislation requires otherwise.

18 REPORTING AND PUBLICATION

18.1 Integrated clinical trial report

Data will be reported in a clinical trial report in compliance with the requirements of the current version of ICH E3: Structure and Content of Clinical Trial Report, ICH GCP Guidelines and ALK SOPs.

The national coordinating investigator(s) will review and sign the clinical trial report.

Clinical trial protocol	Date:	12-Nov-2021	
Trial ID: SU-G-01	Version:	4.0	
EudraCT No. 2020-000455-12	Status:	Final	
CONFIDENTIAL	Page:	71 of 77	

18.2 Publication of results

ALK retains exclusive ownership of all data, results, reports, findings, discoveries and any other information developed or collected during this trial and ALK shall have the exclusive right to use all such information for any purpose, including, but not limited to, use of the results and data either in the form of CRF (or copies of these), or in the form of a report, with or without comments and with or without analysis, in order to submit them to the regulatory authorities of any country.

By signing the investigator agreement, the investigator agrees that the results of this trial may be used for submission to national and/or international registration and supervising authorities. The authorities will be notified of the investigator's name, address, qualifications and extent of involvement.

It is envisaged that the findings of this trial, including sub-analysis, and if relevant the epidemiology of the screened population and the selection process, will, in due time and by mutual agreement, be published in international journals, theses and/or presented at scientific meetings or symposia. All presentations and publications must be reviewed by ALK prior to public presentation or submission. For multi-site trials, it is mandatory that the primary publication is based on data from all trial sites, analysed as stipulated in the protocol and in the SAP.

Authorship is based on the International Committee of the Medical Journal Editors "Uniform Requirements" (Vancouver Declaration). Invitation to author publications will be at the discretion of ALK. All authors of publications need to fulfil all four criteria stated in the Vancouver guidelines/ICMJE criteria: 1) substantial contributions to the conception or design of the work; or the acquisition, analysis, or interpretation of data for the work; 2) drafting the work or revising it critically for important intellectual content; 3) final approval of the version to be published; and 4) agreement to be accountable for all aspects of the work in ensuring that questions related to the accuracy or integrity of any part of the work are appropriately investigated and resolved. Failure to meet all 4 ICMJE criteria will result in removal as author. Other significant contributions to the publication will be acknowledged in accordance with journal or other relevant specific guidelines.

If the number of authors is restricted, selection will be based on accountability for the conduct and reporting of the trial.

Investigators participating in multi-site trials agree not to present data gathered from one trial site or a group of trial sites before the primary publication has been accepted for publication unless formally agreed by all other investigators and ALK.

ALK shall be provided with copies of any proposed publication or presentation at least 60 days in advance of the submission of such proposed publication or presentation to a journal, editor, or other third party. ALK has the right to review and comment on any such publication or presentation within 60 days of receipt but cannot prevent publications of findings. The investigator agrees that all reasonable comments made by ALK will be incorporated into the publication. Furthermore, the investigator agrees that the investigator shall, at ALK's request exclude or delete any confidential information, except trial results generated hereunder, from the proposed publication or presentation.

Furthermore, results of the trial will be posted in the EU Clinical Trials Registry no later than 12 months after LSLV. No individual de-identified subject data will be shared. Results of the trial, together with the protocol and SAP, will be posted at ClinicalTrials.gov together with the final protocol and SAP no later than 12 months after the primary completion date. No individual de-identified subject data will be shared.
Clinical trial protocol	Date:	12-Nov-2021	
Trial ID: SU-G-01	Version:	4.0	
EudraCT No. 2020-000455-12	Status:	Final	
CONFIDENTIAL	Page:	72 of 77	

If results are not disclosed on external websites in accordance with international and national regulations, a justification must be given.

19 FINANCE AND INSURANCE

ALK subscribes to an insurance policy covering, in its terms and provisions, it is legal liability for injuries caused to participating subjects and arising out of these trial assessments performed strictly in accordance with this protocol as well as with applicable law and professional standards.

The compensation to the investigators for work performed under this protocol will be set out in separate clinical trial agreements with the investigators.

20 TRIAL ORGANISATION

The title, name, address and contact details of investigators and clinical research organisations (CROs) and e.g. subcontractors for project management, monitoring, central laboratory, etc. are listed in Appendix 3: Trial organisation.

Clinical trial protocol	Date:	12-Nov-2021	
Trial ID: SU-G-01	Version:	4.0	
EudraCT No. 2020-000455-12	Status:	Final	
CONFIDENTIAL	Page:	73 of 77	

Table 11 Symptom relieving medication for rhinitis with/without conjunctivitis	.35

EudraCT No.: 2020-000455-12 Status: Final CONFIDENTIAL Page: 6 of 47	Statistical analysis plan Trial ID: SU-G-01 EudraCT No.: 2020-000455-12 CONFIDENTIAL	Date: Version: Status: Page:	27-Oct-2023 1.0 Final 6 of 47		K
--	---	---------------------------------------	--	--	---

Version history This statistical analysis plan (SAP) for trial SU-G-01 is based on protocol version 4.0 dated 12-Nov-2021.

SAP Version	Date	Change	Rationale
1	12-JUL-2023	Not applicable	Original version

1 List of abbreviations

AAS	Asthma analysis set
AE	Adverse event
AIT	Allergy immunotherapy
ALT	Alanine aminotransferase
ARC	Allergic rhinoconjunctivitis
AST	Aspartate aminotransferase
ATS	American Thoracic Society
BP	Blood pressure
BUN	Blood urea nitrogen
DBL	Database lock
DMS	Daily medication score
DPS	Data points sets
DSS	Daily symptom score
eCRF	Electronic case report form
EGPS	Entire grass pollen season
EMA	European medicines agency
ESI	Events of special interest
EudraCT	European Union Drug Regulating Authorities Clinical Trials
FAS	Full analysis set
FEV ₁	Forced expiratory volume in 1 second
FVC	Forced vital capacity
GCP	Good clinical practice
GLMM	Generalised linear mixed model
ICH	International Conference on Harmonisation of Technical Requirements for Registration of Pharmaceuticals for Human Use
ICS	Inhaled corticosteroids
IE	Intercurrent event
lgE	Immunoglobulin E

IMP	Investigational medicinal product
ITT	Intention-to-treat
IRT	Interactive response technology
LABA	Long-acting bronchodilator inhalers
LDH	Lactate dehydrogenase
LSLV	Last subject last visit
MAR	Data missing at random
MCAR	Missing completely at random
MCH	Mean corpuscular haemoglobin
MCID	Minimal clinically important difference
MCV	Mean corpuscular volume
MedDRA	Medical Dictionary for Regulatory Activities
MMRM	Mixed-effect model for repeated measurement
MNAR	Data missing at not random
PGPS	Peak grass pollen season
рН	Potential of hydrogen
PRO	Patient reported outcome
PT	Preferred term
RQLQ	Rhinitis quality of life questionnaire
SABA	Short-acting β ₂ -agonist
SAE	Serious adverse event
SAP	Statistical analysis plan
SAF	Safety analysis set
SAS®	Computer software for statistical programming
SD	Standard deviation
SGOT	Serum glutamic-oxaloacetic transaminase
SGPT	Serum glutamic pyruvic transaminase
SLIT	Sublingual immunotherapy
SOC	System organ class
SPT	Skin prick test
TCS	Total combined score
TEAE	Treatment emergent adverse event
TOS	Total analysis set
WHO	World Health Organization

2 Table of definitions

AE	An AE is any untoward medical occurrence in a clinical trial subject, and which does not necessarily have a causal relationship with the administered IMP.
Completed treatment	A subject is considered to have completed treatment if he/she has been randomized and has not discontinued treatment.
Completed subject	A randomised subject is considered completed if he/she has not discontinued the trial before V9.
Completion date	For each completed subject, the date of the last scheduled procedure/end of trial visit(V9).
Concomitant medication	All medications being continued by a subject on entry into the trial and all medications given in addition to the background treatment during the trial.
Date of last contact	Date of the last contact, either by telephone or in a visit.
End of trial	The end of the trial is defined as the date of V9.
Estimand	A precise description of the treatment effect reflecting the clinical question of interest posed by the trial objective. It summarises at a population-level what the outcomes would be in the same patients under different treatment conditions being compared (ICH 2020).
Grass pollen season	Start date: The first day of 3 consecutive days with (non-missing) pollen count larger than or equal to 10 grains/m ³ .
	 Stop date: The last day before 3 consecutive days with (non-missing) pollen count less than 10 grains/m³.
Peak grass pollen season	The 15 days period with the highest average pollen count during the entire grass pollen season.
IMP	A pharmaceutical form of an active substance or placebo being tested or used as a reference in a clinical trial, including products with a marketing authorisation used or assembled (formulated or packaged) in a way different from the authorised form, or when used for an unauthorised indication, or when used to gain further information about the authorised form.
Intercurrent events	Events occurring after treatment initiation that affect either the interpretation or existence of the measurements associated with the clinical question of interest. It is necessary to address intercurrent events when describing the clinical question of interest in order to precisely define the treatment effect that is to be estimated (ICH 2020).
LSLV	Last scheduled physical visit for any subject (V9).
Primary trial completion date	Date of the last data collection for the primary endpoint (ClinicalTrials.gov) is the last scheduled physical visit for any subject (V9).
Rescue medication	Medicinal products provided by ALK when the efficacy of the IMP is not sufficient or likely to cause an AE to the subject or to manage an emergency situation in relation to grass pollen allergy symptoms in agreement with the EMA Definition of IMPs and Use of AMPs Consultation Document (EMA 2016)
	The rhinoconjunctivitis rescue medication in this trial is:
	Antihistamine tablets
	Antihistamine eye drops
	Corticosteroid nasal spray.
Source documents	Source documents are original documents, data, and records from which the subjects' electronic case report form (eCRF) data are obtained. These include, but are not limited to, hospital records (from which medical history and

	concomitant medication may be summarised into the eCRF), clinical and office charts, laboratory and pharmacy records, diaries, microfiches, radiographs, and correspondence.
Systemic corticosteroids	Oral, intramuscular, or intravenously administered corticosteroids.
TEAE	TEAEs are defined as AEs with start date and/or time on or after the time of first IMP administration and no later than 7 days after last IMP administration.
Trial completion	The trial is completed once the CSR is signed.
Withdrawal from trial date	Date of subject withdrawal from trial. In case of subjects lost to follow-up, the withdrawal date is defined as the date the investigator/sponsor decides to withdrawal the subject.

3 Introduction

The SAP supplements the statistical section in the protocol and provides additional details regarding estimands, analysis sets, endpoints and statistical analyses. In Section 9.1 detailed descriptions of pollen seasons, derivation of endpoints, imputation of dates, and the statistical analyses are provided. In supplementary document to the SAP: Documentation of Trial Analysis Sets, the various subject related listings are provided.

Changes to the analyses and changes that might (or can) impact the analyses described in the protocol are documented in Section 6.5.

This SAP has been written and approved before database lock and unblinding.

3.1 Objectives and endpoints

Objectives	Endpoints
Primary	
The primary objective is to compare the efficacy of 5-grass mix SLIT-drops to placebo in relieving grass rhinoconjunctivitis symptoms and on the use of symptom-relief medication during the 2 nd PGPS.	The primary efficacy endpoint is the average daily allergic rhinoconjunctivitis TCS during the 2 nd PGPS
Key secondary	
To measure the impact of treatment with 5- grass mix SLIT-drops compared to placebo on health-related quality of life as a result of grass pollen-induced rhinoconjunctivitis during the 2 nd PGPS.	The average weekly overall RQLQ score during the 2 nd PGPS.
To compare the efficacy of 5-grass mix SLIT- drops to placebo in relieving grass rhinoconjunctivitis symptoms and on the use of symptom-relief medication during the 1 st PGPS.	The average daily allergic rhinoconjunctivitis TCS during the 1 st PGPS.
To measure the impact of treatment with 5-	The average weekly overall RQLQ score

Γ			
grass mix SLIT-drops compared to placebo on health-related quality of life as a result of their grass pollen-induced rhinoconjunctivitis during the 1 st PGPS.	during the 1 st PGPS.		
Supportive secondary			
To measure the impact of treatment with 5- grass mix SLIT-drops compared to placebo on health-related quality of life as a result of their grass pollen-induced rhinoconjunctivitis during the 1st - EGPS and during the 2nd EGPS.	 The average weekly overall RQLQ score during the 1st EGPS. The average weekly overall RQLQ score during the 2nd EGPS. 		
To compare the efficacy of 5-grass mix SLIT- drops to placebo in relieving grass rhinoconjunctivitis symptoms and in use of symptom-relief medication during the 1st EGPS and during the 2nd EGPS.	 The average daily allergic rhinoconjunctivitis TCS during the 1st EGPS. The average daily allergic rhinoconjunctivitis TCS during the 2nd EGPS. 		
To compare the efficacy of 5-grass mix SLIT- drops to placebo in relieving grass rhinoconjunctivitis symptoms during the 1st and during the 2nd PGPS, and during the 1st EGPS and during the 2nd EGPS.	 The average daily allergic rhinoconjunctivitis DSS during the 1st PGPS. The average daily allergic rhinoconjunctivitis DSS during the 2nd PGPS. The average daily allergic rhinoconjunctivitis DSS during the 1st EGPS. The average daily allergic rhinoconjunctivitis DSS during the 1st EGPS. The average daily allergic rhinoconjunctivitis DSS during the 2nd PGPS. 		
To compare the efficacy of 5-grass mix SLIT- drops to placebo in use of symptom-relief medication during the 1st and during the 2nd PGPS, and during the 1st and during the 2nd EGPS.	 The average daily allergic rhinoconjunctivitis DMS during the 1st PGPS. The average daily allergic rhinoconjunctivitis DMS during the 2nd PGPS. The average daily allergic rhinoconjunctivitis DMS during the 1st EGPS. The average daily allergic rhinoconjunctivitis DMS during the 1st EGPS. The average daily allergic rhinoconjunctivitis DMS saduring the 2nd EGPS. 		
To measure (or compare) the safety and tolerability of 5-grass mix SLIT-drops and (or to) placebo. To measure safety and treatment tolerability of patients who have grass pollen- induced rhinoconjunctivitis and who receive	TEAEsESIsIMP-related TEAEs		

either 5-grass mix SLIT-drops or placebo at	Treatment-emergent SAEs
randomisation and at the end of trial.	• TEAEs leading to discontinuation of treatment (using definitions of reasons for discontinuing treatment as in estimand framework in section 6.1.2)
	• Time to discontinuation of treatment due to TEAEs (using definitions of reasons for discontinuing treatment as in estimand framework in section 6.1.2)
	Vital signs during the trial
	 Physical examination at randomisation and end of trial
	Lung function tests at randomisation
	Clinical laboratory assessments at randomisation and end of trial
Exploratory	

 Date:
 27-Oct-2023

 Version:
 1.0

 Status:
 Final

 Page:
 12 of 47

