5.2 Discontinuation from trial

The subject will be advised in the informed consent form that he/she has the right to discontinue from the trial at any time without prejudice.

Subjects must be discontinued from the trial under the following circumstances:

Clinical trial protocol	Date:	12-Nov-2021	
Trial ID: SU-G-01	Version:	4.0	
EudraCT No. 2020-000455-12	Status:	Final	
CONFIDENTIAL	Page:	31 of 77	

- If, in the investigator's opinion, continuation in the trial would be detrimental to the subject's well-being
- If informed consent is withdrawn

If found required by ALK after discussion with the investigator, subjects may be discontinued from the trial under the following circumstances:

- If subject is treated with prohibited medication as defined in Table 2
- In case of protocol deviation, violation of eligibility criteria or deviation from the treatment plan specified in the protocol (e.g. incorrect administration of the IMP)
- Simultaneous or previous participation (within 30 days of randomisation) in other clinical trials of an approved or non-approved investigational medicinal product

In case a subject discontinues from the trial, the discontinuation page in the electronic case report form (eCRF) should be completed. On the discontinuation page the investigator should record the date of the discontinuation from the trial, the person initiating the discontinuation, and the primary reason for discontinuation. If an adverse event (AE) is involved in a discontinuation, this must be recorded as the primary reason. In all cases, the primary reason for discontinuation must be recorded in the eCRF and in the subject's medical records. A follow-up visit on the subject is necessary to establish trial-related AEs that must be reported in accordance with the appropriate procedures.

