6.1.2 IMP discontinuation

As pointed to previously, reasons for discontinuation of IMP will be categorised into three categories: 1) due to "IMP-related AE" 2) due to "lack of efficacy" and 3) due to "other reasons". As the eCRF defined that trial- and treatment discontinuation reasons are not corresponding to this tripartite split the following mapping form the observed data in the eCRFs to the three categories will be performed:

Treatment discontinuation reasons presented in the eCRF's "Visit Status"-form are:

• Severe or persistent symptoms of eosinophilic oesophagitis

- Pregnancy
- Physician's decision
- Adverse event(s)
- Asthma difficult to control
- Treatment is unblinded

while withdrawal from trial reasons presented in eCRF's "End of study"-form are:

- Screening failure
- Withdrawal of consent
- Adverse event(s)
- Lost to follow-up
- Non-compliance with protocol
- Pregnancy
- Death
- Lack of efficacy
- Randomisation code broken
- Other

Before DBL, the discontinuation of treatment is re-defined and the subject specific list of discontinuations and their classifications to fit the estimand framework is in supplementary document to the SAP: Documentation of Trial Analysis Sets.

Discontinuation due to AEs

A subject is considered discontinued from the treatment due to IMP-related AE if the following conditions are met:

- 1. If, in the "Visit status"-form or End of study"-form reported reason for treatment discontinuation or withdrawal from trial is:
 - Severe or persistent symptoms of eosinophilic oesophagitis
 - Adverse event(s)
 - Asthma difficult to control
- 2. And AEs related to discontinuation are classified as possibly or probably related.

Discontinuation due to lack of efficacy

A subject is considered discontinued from the treatment due to lack of efficacy if the following conditions are fulfilled:

1. If, in the "End of study"-form, it is noted that the subject withdrawal from trial due to "Lack of efficacy".

Discontinuation due to "other reasons"

A subject is considered discontinued from the treatment due to other reasons if the subject discontinues treatment or withdrawal from trial due to other reasons than mentioned above.

Date: 27-Oct-2023 Version: 1.0 Status: Final Page: 21 of 47

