6.4.2.2 Reporting of adverse events

All TEAEs will be summarised by treatment group according to causality (IMP related or not), severity (mild, moderate, severe), seriousness (yes/no), action taken, outcome (recovered or resolved / recovered or resolved with sequelae / not recovered or not / resolved / fatal / unknown), and whether the event led to IMP discontinuation and interruption. The number of subjects in treatment group, the frequency and proportion of subjects having the event, as well as the number of events and proportion of events will be displayed. A similar summary table will be produced for all IMP-related TEAEs.

All TEAEs and all IMP-related TEAEs will be summarised (in separate tables) by treatment group, SOC, and PT, displaying number of subjects in treatment group, and number and frequency of subjects having the event. The tables will be sorted according to most frequent SOC and PT in the active treatment group, and the most common TEAEs defined as those that are present in at least 2% of subjects in the active treatment group will be marked.

Severe TEAEs will be listed only if there are fewer than 10 events in total. Otherwise, severe TEAEs will also be summarised and presented by SOC and PT similar to how TEAEs are presented. The same follows for SAEs, TEAEs leading to IMP discontinuation, and IMP-related TEAEs leading to IMP interruption.

For most frequent IMP-related TEAEs (present in at least 2% of subject in the active treatment group) onset and duration will be presented as follows: time to onset and average duration both in days, will be presented by SOC and PT and treatment. In addition, for day 1 of treatment average time to onset in minutes will be presented by SOC PT and treatment.

In addition, most frequent non-serious TEAEs reported in at least 5% of subjects in any treatment group by SOC and PT.

For the most frequent IMP-related TEAEs which are recurrent, the average daily duration and the average duration in days from first to last occurrence will be presented by PT and treatment.

A table with the overall summary of the safety profile will be produced showing number of subjects with TEAEs, IMP-related TEAEs, IMP-related severe TEAEs, IMP-related treatmentemergent SAEs, IMP-related TEAEs leading to IMP discontinuation and each type of IMPrelated treatment-emergent ESI by treatment group.

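### SAP 3.1 defines two safety endpoints on stopping treatment for TEAEs through the imputation categories of 6.1.2, whose only adverse-event category is IMP-related; this conflicts with 6.4.2.2 and 8.3

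*SAP*

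**What the plan says.** SAP 3.1 gives, under the safety and tolerability objective, the endpoint "TEAEs leading to discontinuation of treatment (using definitions of reasons for discontinuing treatment as in estimand framework in section 6.1.2") and the companion endpoint "Time to discontinuation of treatment due to TEAEs (using definitions of reasons for discontinuing treatment as in estimand framework in section 6.1.2"). The same list has TEAEs and IMP-related TEAEs as separate entries.

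SAP 6.1.2 states that "reasons for discontinuation of IMP will be categorised into three categories": IMP-related AE, lack of efficacy and other reasons. The AE category has two conditions. The eCRF reason must be adverse event(s), oesophagitis symptoms or asthma that is hard to control. The second condition reads "And AEs related to discontinuation are classified as possibly or probably related". A subject goes to the residual category "if the subject discontinues treatment or withdrawal from trial due to other reasons than mentioned above".

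SAP 6.4.2.2 sets out the safety reporting. Severe TEAEs are listed if there are fewer than 10 and otherwise tabulated by SOC and PT, and then: "The same follows for SAEs, TEAEs leading to IMP discontinuation, and IMP-related TEAEs leading to IMP interruption". The overall safety table in that section carries IMP-related TEAEs leading to IMP discontinuation as its own item. The band plot in SAP 8.3 shows discontinuation for AE, with no reference to relatedness.

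**The concern.** The stated objective is to measure or compare safety and tolerability against placebo. For that comparison, AE discontinuation counted regardless of causality does not depend on the investigator's attribution. A related-only count does. The categories in 6.1.2 serve another purpose: they decide which arm a missing efficacy score is imputed from, and SAP 6.5 describes the re-classified reasons as being for the estimand framework. Taking them into a safety endpoint turns what is named as TEAEs leading to discontinuation into IMP-related TEAEs leading to discontinuation, and the SAP gives no reason for doing so.

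At stake is what two declared safety endpoints mean. Protocol 5.1 makes asthma that becomes difficult to control a mandatory reason to stop IMP. Under 6.1.2 such a stop counts as an AE discontinuation only if the event is also judged related.

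**Working it through.** The point rests on no sample size, power or alpha figure, so there is nothing to reproduce. The check is to follow one subject through the plan.

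**The subject.** Stops IMP with the eCRF reason adverse event(s). The event is treatment-emergent and the investigator grades it Unlikely. The causality scale in Protocol 12.2.2 has only Possible and Unlikely. SAP 6.1.2 speaks of possibly or probably related, so Unlikely is the grade it leaves out.

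1. **SAP 6.1.2.** The first condition of the AE category is met and the second is not. The subject did not withdraw for lack of efficacy. Result: other reasons.
2. **SAP 3.1, TEAEs leading to discontinuation, read through 6.1.2.** Not an event.
3. **SAP 3.1, time to discontinuation due to TEAEs, read through 6.1.2.** Not an event. The SAP does not say how such a subject is handled at the stopping date.
4. **SAP 6.4.2.2, TEAEs leading to IMP discontinuation.** Included, because no relatedness limit is stated. The summary of all TEAEs also classifies each event by whether it led to IMP discontinuation, with causality as a separate item.
5. **SAP 6.4.2.2, overall safety table, IMP-related row.** Not included, correctly.
6. **SAP 8.3, band plot.** Included in the AE band.
7. **SAP 8.3, added summary by estimand-framework reason.** Shown under other reasons, as that summary is labelled to do.

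Steps 2 and 4 give opposite answers for the same subject on what is nominally the same endpoint. Step 3 has no counterpart in 6.4, which describes no analysis of time to discontinuation due to TEAEs. The closest output is the band plot in step 6. Protocol 15.4 plans a Kaplan-Meier plot of time to discontinuation, but for all causes, so it does not define the AE endpoint either.

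**Size.** The number of subjects affected is the number of AE stops multiplied by the share judged unrelated. The documents give no such share, so it could be anything from 0 to 100%. The planning figure of 4.5% per year discontinuing for AEs (Protocol 15.2, SAP section 7) does not help, because neither document says whether it is all-cause or related-only. No count is derived here.

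**The case against.** The strongest reply is that the all-causality comparison is already planned. SAP 6.4.2.2 summarises and lists TEAEs leading to IMP discontinuation by arm without a relatedness limit, and it has the IMP-related row. SAP 8.3 reports the reasons for IMP discontinuation and adds the estimand categories as an extra. This stands. A reader might infer from 3.1 that unrelated AE stops vanish from the report, or that the AE discontinuation rate will be understated. The documents do not support either inference, because the unfiltered results are to be reported. Nor is it shown that two safety tables must disagree: no table in 6.4 is specified on the 6.1.2 categories.

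A reader might also see a conflict with Protocol 5.2: "If an adverse event (AE) is involved in a discontinuation, this must be recorded as the primary reason". There is none. That sentence tells the investigator what to record when a subject leaves the trial. Section 6.1.2 starts from the recorded reason and groups it for analysis.

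A third reply is that the reference in 3.1 may mean only the mapping across the two eCRF forms, since SAP 6.5 says IMP discontinuation was not collected in a suitable way. The omission of IMP-related from the endpoint names fits that reading. But the text invokes the definitions of reasons, and the only AE reason defined there carries the relatedness condition. If the narrower meaning was intended, the SAP should say so.

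Finally, these are supportive endpoints outside multiplicity control (SAP 4.1), and no efficacy conclusion depends on them. That limits the importance of the point but does not remove it.

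**Conclusion.** The point holds as an inconsistency in the definition of two declared safety endpoints. Followed literally, SAP 3.1 with 6.1.2 excludes AE stops judged unrelated from both. For TEAEs leading to discontinuation, 6.4.2.2 and 8.3 contradict that restriction, so the endpoint has two definitions. For "Time to discontinuation of treatment due to TEAEs" section 6.4 offers no other definition or analysis, so the restriction to related AEs stands unless the text is changed. This second endpoint is the more serious part.

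The conclusion rests on the literal reading of the reference in 3.1. Its numerical effect cannot be derived from the documents. It does not extend to a claim that events are lost from the safety report or that the reported rate is too low.

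**What to change.** In SAP 3.1, delete the reference to 6.1.2 from both endpoints and define them on all TEAEs leading to IMP discontinuation, regardless of causality, in line with 6.4.2.2 and 8.3. Keep the IMP-related subset as a separate summary; for the first endpoint the overall safety table already has it. Add a short description to 6.4 of how time to discontinuation due to TEAEs will be analysed, including how stops for other reasons are handled. State in 6.1.2 that its categories are for estimand imputation, with the added disposition summary in 8.3 labelled accordingly, as it already is.

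The cost is two edited endpoint lines and a few sentences. No new data are needed: 6.4.2.2 already relies on a per-event indicator of whether the AE led to IMP discontinuation, and 6.4.1 already uses the date of last IMP intake. If the SAP is not reissued, Protocol section 15 provides for changes from the final SAP to be documented in the clinical trial report.
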